2.6.2.5 Laboratory data

Grading of laboratory values will be assigned programmatically as per CTCAE version 4.03. The calculation of CTCAE grades will be based on the observed laboratory values only, clinical assessments will not be taken into account.

CTCAE Grade 0 will be assigned for all non-missing values not graded as 1 or higher. Grade 5 will not be used.

For laboratory tests where grades are not defined by CTCAE 4.03, results will be categorized as low/normal/high) based on laboratory normal ranges.

The following summaries will be produced for hematology and biochemistry laboratory data (by laboratory parameter and treatment):

- Worst post-baseline CTC grade (regardless of the baseline status). Each patient will be counted only for the worst grade observed post-baseline;
- Shift tables using CTC grades to compare baseline to the worst on-treatment value;
- For laboratory tests where CTC grades are not defined, shift tables using the low/normal/high/(low and high) classification to compare baseline to the worst on-treatment value;

The following listing(s) will be produced for the laboratory data:

- Listing of all CTC grade 3 or 4 laboratory toxicities.

Liver function parameters

Liver function parameters of interest are total bilirubin (TBL), ALT, AST, and alkaline phosphatase (ALP). The number (%) of patients with worst post-baseline values as per Novartis Liver Toxicity guidelines will be summarized:

The following summaries will be produced:

- ALT or AST > 3xULN
- ALT or AST > 5xULN
- ALT or AST > 8xULN
- ALT or AST > 10xULN
- ALT or AST > 20xULN
- TBL > 2xULN
- TBL > 3xULN
- ALT or AST > 3xULN & TBL > 2xULN
- ALT or AST > 3xULN & TBL > 2xULN & ALP < 2xULN (*potential Hy's law*)

Potential Hy's Law events are defined as those patients with concurrent occurrence of AST or ALT > 3xULN and TBL > 2xULN and ALP < 2xULN in the same assessment sample during the on-treatment period. Further medical review should be conducted to assess potential confounding factor such as, liver metastases, liver function at baseline etc.

For more details and adaptation of above summary, Oncology Hepatic Safety guidance should be referred.

2.6.2.6 Other safety data

2.6.2.6.1 ECG and cardiac imaging data

In case the study requires ECG replicates at any assessment, the average of the ECG parameters at that assessment should be used in the analyses.

12-lead ECGs including PR, QRS, QT, QTcF, QTcB, and RR intervals will be obtained centrally/locally for each patient during the study. ECG data will be read and interpreted centrally/locally.

The following summaries will be presented:

- Change from baseline for ECG parameters by timepoint
- Number and percentage of patients with notable ECG values.
 - QT, QTcF, or QTcB
 - New value of > 450 and ≤ 480 ms
 - New value of > 480 and ≤ 500 ms
 - New value of > 500 ms
 - Increase from baseline of > 30 ms to ≤ 60 ms
 - Increase from baseline of > 60 ms
 - HR
 - Increase from baseline >25% and to a new HR > 100 bpm
 - Decrease from baseline >25% and to a new HR < 50 bpm
 - PR
 - Increase from baseline >25% and to a new PR > 200 ms
 - New PR > 200 ms
 - QRS
 - Increase from baseline >25% and to a new QRS > 120 ms
 - New QRS > 120 ms

A listing of patients with only notable ECG values will be produced. For patients with at least one notable ECG parameter value, all parameters should be listed.

PK-ECG analysis

A linear mixed effects model will be used to analyze QTcF change from baseline versus plasma NIR178 concentration using the PK/ECG analysis set. The linear mixed effects model is as follows:

$$\Delta QTcF_{ij} = (\beta_0 + b_{0i}) + \beta_1 baseline_QTcF_i + \beta_2 concentration_{ij} + \epsilon_{ij}$$

In this model, b_{0i} is the patient's random effect. A compound symmetry covariance structure is assumed; other covariance structures may be explored.

The estimated mean QTcF change from baseline will be presented along with the two-sided 90% CI for different concentration thresholds (mean, Q1, median, and Q3) of C_{max} for dose levels 160mg BID and 240 mg BID, corresponding to C1D1 and/or steady state.

- These thresholds will be determined from C1D1 and/or steady state C_{max}
- Baseline QTcF will be set to its median baseline value

QTcF is suggested by the ICH E14 guidance (attached at the end of this document (Section 6)) and is more accurate than other correction methods in patients with altered heart rates. [REDACTED]

[REDACTED]

A check of mean concentration versus time and mean QTcF change from baseline versus time should be performed to rule out any delayed effect (hysteresis). [REDACTED]

[REDACTED]

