1.2.1.4.1 Clinical pharmacokinetics of NIR178

The pharmacokinetics of NIR178 both single and repeat dose of NIR178 has been characterized in healthy volunteers in prior studies as well as in NSCLC patients in an ongoing Phase I/Ib study (CNIR178X2103J). A mono-oxygenated metabolite (NJI765) was also monitored in healthy volunteer studies. In healthy volunteers, (single ascending dose levels of 10, 20, 40, 80, 160, 320 and 480 mg) NIR178 demonstrated rapid absorption and elimination with a Tmax of 0.17-4 hrs and a terminal elimination half-life of 1.06-3.83 hrs. Concentrations in the systemic circulation were generally below the lower limit of detection at 10 and 20 mg. Systemic exposure (Cmax and AUC) over the dose range of 40 to 480 mg generally increased more than proportionally with dose; inter-subject variability was moderate to high.

In the Phase I/Ib study in advanced NSCLC, patients were dosed NIR178 orally twice daily (BID) as a single agent 80, 160, 320, 480, and 640mg. NIR178 was rapidly absorbed with a median Tmax occurring at 2 hours post-dose. NIR178 featured nonlinear pharmacokinetics, both dose- and time-dependent. Similarly to healthy volunteers, NIR178 systemic exposure increased more than proportionally with dose following single and repeated BID dosing of 80 to 640 mg. Despite of its short terminal half-life, the accumulation ratio of NIR178 was approximately 3-fold after one week of multiple daily dosing compared to a single dose. Inter-subject variability in Cmax and AUC was moderate to high. The pharmacokinetics of NIR178 (160, 240, and 320 mg BID) when given in combination with PDR001 (400 mg every 4 weeks) in patients with advanced NSCLC is largely similar to that of NIR178 alone, suggesting no clinically relevant interaction between the two drugs.

Please refer to the [NIR178 (PBF-509) Investigator's Brochure] for further details.

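### The PK-ECG model has a random intercept but no random concentration slope, so its 90% CIs for mean QTcF change at Cmax are too narrow if patients differ in slope

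*SAP*

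**What the plan says.** The PK-ECG analysis in SAP 2.6.2.6.1 regresses QTcF change on baseline QTcF and NIR178 concentration. The displayed equation attaches the patient term to the intercept, and the text confirms it: "In this model, b_{0i} is the patient's random effect". The concentration coefficient carries no patient index. On covariance: "A compound symmetry covariance structure is assumed; other covariance structures may be explored". No alternative structure is named, and nothing says when one would be tried or which result would be reported.

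The output is defined thus: "The estimated mean QTcF change from baseline will be presented along with the two-sided 90% CI for different concentration thresholds". These are "mean, Q1, median, and Q3) of C_{max} for dose levels 160mg BID and 240 mg BID, corresponding to C1D1 and/or steady state". A hysteresis check is planned. The visible text gives no QTc margin and no rule for using the upper limit. Two stretches of text inside this analysis are redacted, one after the sentence justifying QTcF and one after the hysteresis check.

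Protocol 1.2.1.4.1 supplies the relevant pharmacokinetics: "Inter-subject variability in Cmax and AUC was moderate to high", and "the accumulation ratio of NIR178 was approximately 3-fold after one week of multiple daily dosing compared to a single dose".

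**The concern.** A random intercept with independent residuals already implies compound symmetry, so the covariance sentence adds nothing to the model, although it does no harm. What matters is the absent term. With one common slope, several ECGs from a patient who is more QTc-sensitive than average count as separate evidence about that slope. The model-based standard error then omits between-patient slope variance. The omitted part grows with the concentration at which the mean is read, so it is largest at the high Cmax values that a QTc assessment looks at.

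The CI is the product of this analysis. If it is too narrow, its upper limit sits too low and the result looks more reassuring than the data warrant.

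A smaller point concerns where the CI is read. The wording "corresponding to C1D1 and/or steady state" would be satisfied by Day 1 alone, although the drug accumulates on repeated dosing.

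**Working it through.** The documents state no CI width, coverage or margin for this analysis, so there is no figure to reproduce. The check is a Monte Carlo study of the stated model.

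**Inputs from the documents**
- 257 patients with time-matched PK and ECG at 3 August 2020: 244 at 160 mg BID and 13 at 240 mg BID (Protocol, Amendment 6 rationale).
- ECG times from Protocol Table 7-7. The dense pattern (pre-dose, 0.5, 1, 2, 3 and 4 h) is still listed for Schedules 2 and 3 and is assumed for the earlier extensive sampling.
- Two-sided 90% CI, so z = 1.645 and each limit should miss 5% of the time.

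**Assumptions (not in the documents)**
- Mean slope 5 ms per mean steady-state 160 mg Cmax (set to c = 1).
- Slope SD 0, 1.25, 2.5 or 5 ms, that is 0, 25, 50 or 100% of the mean slope.
- Intercept SD 7 ms and residual SD 8 ms.
- Lognormal concentrations with CV 60%; 16 matched records per patient.
- 240 mg Cmax at c = 1.5, which is dose-proportional. Protocol 1.2.1.4.1 says exposure rises faster than that.

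**Models**
- Data: ΔQTcF = (β0 + b0i) + β1·baseline + (β2 + b1i)·concentration + ε.
- Analysis: the SAP model, which omits b1i, by REML with model-based SE. Half-width = 1.645 × SE.

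**Results, 1000 trials per cell**

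| Slope SD / mean | Coverage at 160 / 240 mg Cmax | Upper limit too low at 160 / 240 mg |
|---|---|---|
| 0% | 89.0% / 90.4% | 4.7% / 5.5% |
| 25% | 88.5% / 89.0% | 6.3% / 5.3% |
| 50% | 86.2% / 82.6% | 7.1% / 8.1% |
| 100% | 73.8% / 67.1% | 14.2% / 15.8% |

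Monte Carlo error is about 1 to 1.5 percentage points. Bias in the estimated mean is 0.1 ms or less, so the fault lies in the SE.

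**Cross-check at slope SD 100%.** At 160 mg Cmax the mean model SE is 0.52 ms and the true SD of the estimate is 0.76 ms. Expected coverage is 2Φ(1.645 × 0.52/0.76) − 1 = 2Φ(1.126) − 1 = 74%, as simulated. At 240 mg, SE 0.62 and SD 1.06 give 2Φ(0.962) − 1 = 66%, against 67% simulated.

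**Size in ms at slope SD 100%,** comparing the model SE with a patient-clustered (sandwich) SE:
- 160 mg: 1.645 × 0.52 = 0.86 against 1.645 × 0.71 = 1.17, a shortfall of 0.3 ms.
- 240 mg: 1.645 × 0.62 = 1.02 against 1.645 × 1.00 = 1.64, a shortfall of 0.6 ms.

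**Q3 of Cmax.** For a lognormal with CV 60%, σ = √ln(1.36) = 0.5545 and Q3/mean = exp(0.6745 × 0.5545 − 0.5545²/2) = 1.25. So Q3 lies at c = 1.25 for 160 mg and 1.5 × 1.25 = 1.87 for 240 mg. The second value falls between the 240 mg cell above and a further cell at c = 2.25, where slope SD 100% gives 62% coverage and half-width 1.33 against 2.41 ms.

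**Sensitivity**
- Dense or reduced sampling with concentration CV 50% or 80%: coverage 82–91% at slope SD 50% and 68–81% at 100%.
- Most extreme cell (mean slope 10, slope SD 10, 240 mg Cmax): coverage 48%, half-width 1.11 against 2.77 ms.

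**With the remedy, slope SD 100%**
- Clustered SE: 87% coverage at 160 mg and 89% at 240 mg.
- Random slope at 160 mg (150 trials): 89% coverage with half-width 1.05 ms, against 71% and 0.86 ms for the SAP model in the same run.

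**The case against.** The strongest case against is that this is a modelling preference in a supportive analysis. Concentration-QTc modelling is not a listed objective in Protocol Table 3-1 or SAP Table 1-1. The loss depends on a slope SD that nobody has stated, and coverage stays near nominal at 25% of the mean slope. Even in the adverse cells the shortfall is mostly about 1 ms or less, while the SAP's categorical criteria count increases above 30 and 60 ms. The SAP also lets other covariance structures be explored, and the redacted text may contain a random-slope or robust analysis. All of this stands. It limits the size and urgency of the point, but it does not make the stated interval correct.

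Three stronger readings are tempting and are not supported:
- A reader might infer that a QTc safety conclusion is wrong. The visible text states no margin or decision rule, so none can be shown to change.
- A reader might quote coverage for the slope coefficient itself, which is worse (77% at slope SD 50%, 58% at 100%). The SAP's listed output is the mean change at Cmax, where the loss is milder.
- A reader might infer that the exposures of most concern are ignored. The model is read at Q3 of 240 mg Cmax, and individual extremes appear in the counts and listing of notable ECG values. The SAP also names steady state explicitly. The 3-fold accumulation comes from another study with a different capsule (Protocol 2.3), and the text does not tie it to Cmax.

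**Conclusion.** The point holds for the visible primary model. If concentration-QTcF slopes vary between patients, the planned 90% CIs for mean QTcF change at Cmax are too narrow and their upper limits too low. The effect is negligible when the slope SD is a quarter of the mean slope and modest at a half. It is material for coverage when the two are equal, yet still only about 0.3 to 0.6 ms of half-width at mean 160 and 240 mg Cmax. These sizes rest on the assumed slope SD, effect size, variability and sampling pattern. A conclusion would change only if the upper limit lay within that distance of a margin, and none is given. The study has also closed for lack of sufficient efficacy (SAP section 4). This is an inexpensive improvement to a safety analysis; it does not show that the analysis misleads.

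**What to change.** In SAP 2.6.2.6.1:
- Pre-specify a random intercept and a random concentration slope per patient, with unstructured 2×2 covariance. If the slope variance is estimated as zero or the fit fails, revert to the random intercept with patient-clustered (empirical) standard errors. This replaces the compound-symmetry sentence.
- Make steady-state Cmax the main evaluation point and Day 1 supportive. Take it from each schedule's own PK profile day in Protocol Tables 7-9 to 7-11: C1D28 for continuous dosing, C1D14 for Schedule 2 and C1D7 for Schedule 3. A blanket C1D28 rule would not fit Schedules 2 and 3, which hold 40 of the 62 Part 2 patients.
- A percentile above Q3 may be added where numbers allow. At 240 mg it would have rested on 13 patients at August 2020.
- State how the upper limit will be used.

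The cost is SAP wording and one model statement, with no new data. The CIs become slightly wider if slopes vary. The fit may not converge, which the fallback handles.

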2.6.2.6.2 Vital signs

Vital sign assessments are performed in order to characterize basic body function. The following parameters will be collected: weight (kg), body temperature (°C), heart rate (beats per minute), systolic and diastolic blood pressure (mmHg).

The number and percentage of patients with on-treatment notable vital sign values (high/low) will be presented.

A listing of patients with only notable vital sign values will be produced. For patients with at least one notable vital sign parameter value, all parameters should be listed.

For analysis of vital signs, the clinically notable vital sign criteria are provided in [Table 2-5](#) below.

Table 2-5 Clinically notable changes in vital signs

Vital sign (unit)	Clinically notable criteria	
	above normal value	below normal value
Weight (kg)	increase ≥10% from baseline	decrease ≥10% from baseline
Systolic blood pressure (mmHg)	≥180 with increase from baseline of ≥20	≤90 with decrease from baseline of ≥20
Diastolic blood pressure (mmHg)	≥105 with increase from baseline of ≥15	≤50 with decrease from baseline of ≥15
Pulse rate (bpm)	≥100 with increase from baseline of >25%	≤50 with decrease from baseline of > 25%
Body temperature (°C)	≥ 39.1	-

2.6.2.6.3 Additional analyses

Tolerability of study drug treatment will be based on the safety set and assessed by summarizing the number of treatment dose interruptions and dose reductions by part. Reasons for dose interruption and dose reductions will be listed and summarized. Cumulative dose, DI and RDI of each study drug will be summarized by treatment group (for reporting and definitions, see [Section 2.1](#) and [Section 2.4.1](#)).

For Japanese safety run-in study, frequency, severity and seriousness of dose limiting toxicities, AEs, laboratory abnormalities and other safety parameters (ECG, physical exams etc) will be summarized separately from the Phase II study or in a consolidated setting using safety set (see General analysis conventions in [Section 2.1](#)).

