Additionally, as per recommendation of the Japanese Health Authority, a safety run-in part will be conducted in Japanese patients dosed at either 80mg or 160mg BID of NIR178 for the first cycle of treatment. The data generated from the safety run-in is considered adequate to evaluate the safety and pharmacokinetic (PK) profiles of single agent NIR178. Since there were no differences in the safety and PK profiles of PDR001 between Japanese and non-Japanese patients treated at the RDE of 400mg IV Q4 weeks in study CPDR001X1101, and given the low likelihood of DDI between NIR178 and PDR001 ([Section 2.4.1](#)), following the first cycle safety run-in patients who receive single-agent NIR178 will be treated with the combination of NIR178+PDR001 starting cycle 2 onwards ([Section 4.1.4](#)). While the final analysis of safety will use all available safety and pharmacokinetic data (including combination phase with PDR001), the safety of single agent NIR178 in Japanese patients in relation to that of non-Japanese patients treated at the same dose levels in the phase I study CNIR178X2103J, will be the primary determinant of whether or not Japanese patients can join the phase II study. As of Protocol Amendment 6, patients enrolled in the Japanese safety run-in part of the study will be treated with NIR178 240mg hard gelatin capsules BID in combination with PDR001 400mg Q4W starting at Cycle 1 Day 1. Based on the data from the Japanese safety run-in at the 80mg and 160mg, there were no obvious ethnic differences on safety and PK observed between Japanese versus non-Japanese patients. In addition, no DDI has been observed between NIR178 and PDR001. This design also allows Novartis to assess DLT in combination therapy in Japanese patients at the recommended dose.

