Protocol Amendment 6 opened enrollment to Part 3 for exploring the safety and pharmacokinetics of the new FCT formulation of NIR178 160 mg BID at 'continuous' schedule in combination TNBC patients with PD-L1 SP-142 IC score of 0 (<1%). Provision to add another Part 1 treatment indication to Part 3, contingent on Part 1 analysis, was introduced as well.

[figure not shown]
In addition to the Phase II study, a safety run-in study will be conducted in Japanese patients with treatment indications specified in the Phase II study parts to evaluate the safety and pharmacokinetic profiles of NIR178 as a single-agent or in combination with PDR001 ([Figure 1-2](#)). As of Protocol Amendment 6, total 6 patients were treated - 3 with SA NIR178 80mg and 3 with SA NIR178 160mg, during Cycle 1 and with PDR001 initiated at the beginning of Cycle 2. This amendment required administration of NIR178 240 mg BID in combination with PDR001 among all newly enrolled Japanese patients. The dose escalation algorithm is detailed in Section 1.1.4.

Figure 1-11 Study design

- ¹Part 1: Bayesian adaptive signal finding in patients
- ²Prior to Amendment 5, all patients were treated with NIR178 160mg BID + PDR001 400mg Q4W
- ³Interim analysis of ORR using Bayesian adaptive model, Tumors in which treatment is not declared futile continue enrolling up to 30 patients (except for MSS CRC, 20 additional patients will be enrolled in each tumor group (RAS wildtype and RAS mutant))
- ⁴Part 2: NIR+PDR Schedule optimization
- ⁵Part 3: The selected groups will be based on emerging data from part 1, part 2 and latest scientific literature
- * Dose increment criteria to complete part 3 at 160mg BID or increase to 240mg BID

Figure 1-22 Study design- Japanese run-in part (NIR178 Single Agent and NIR178 +PDR001)

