Japanese Safety Run-in: To assess the preliminary safety, and PK of single agent NIR178 and in combination with PDR001 in Japanese patients	Frequency, severity and seriousness of DLTs, AEs, laboratory abnormalities and other safety parameters (ECG, physical exams etc). Plasma concentration time profiles of NIR178/PDR001 and PK parameters.

2 Statistical Methods

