2.1.1.2 Date of first/last administration of a study drug and study treatment

The date of first (last) administration of a study drug is defined as the first (last) date when a non-zero dose of a drug is administered and recorded on the treatment page eCRF. The date of first/last administration of study drug will also be referred as start/end date of study drug.

The date of first (last) administration of study treatment is derived as the first (last) date when a non-zero dose of either component of the treatment (NIR178 or PDR001) was administered and recorded on the DAR eCRF.

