2.1.1.5 On-treatment assessment/event and observation periods

The overall observation period will be divided into three mutually exclusive segments:

pre-treatment period: from day of patient’s first informed consent to the day before first administration of study treatment

on-treatment period: from date of first administration of study treatment to 30 days after date of last actual administration of study treatment (including start and stop date). This period constitutes ***safety follow-up*** on all patients for 30 days after the last administration of study treatment.

post-treatment period: starting at day 31 after the last administration of study treatment. This period will constitute the following follow-up periods:

- ***extended safety follow-up period:*** all patients receiving PDR001 will continue to have safety evaluations for 150 days after the last dose of PDR001 or 30 days after the last dose of NIR178, whichever occurs later.
- ***disease progression follow-up period:*** Patients who discontinue study treatment for any reason other than death, disease progression per confirmed iRECIST or per Cheson (for DLBCL) or per PCWG3 guidance (for mCRPC) while on treatment, clinical deterioration or clinical progression, lost to follow-up, consent withdrawal or study termination, will have tumor evaluation assessments every 8 weeks (+/- 7 days) during the first 40 weeks,

and every 12 weeks (+/- 7 days) thereafter until disease progression, death, loss to follow-up or withdrawal of consent, whichever occurs first.

- **survival follow-up period:** Upon completion of the 150-day safety follow-up or disease progression follow-up, all patients (except for those in Japanese safety run in) will be followed for survival every 12 weeks until any of the following events (whichever occurs first): death, withdrawal of consent, loss to follow-up or at least 24 months from the first dose of study treatment.

Patients enrolled to another clinical study or alternate treatment (Protocol Section 4.3) will not have follow-up for safety, disease progression and survival assessments performed.

If dates are incomplete in a way that clear assignment to pre-, on-, post-treatment period cannot be made, then the respective data will be assigned to the on-treatment period.

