2.6.2 Safety objectives

All safety analyses will be based on the safety set (see [Section 2.2.2](#)), which will be used for presenting summaries and listings by treatment groups and overall patients following the general analysis conventions defined under [Section 2.1](#).

The assessment of safety is based on the type and frequency of AEs as well as on the number of laboratory values that fall outside of pre-determined ranges (CTCAE grading limits or normal ranges as appropriate). Other safety data include electrocardiogram and vital signs.

All safety reporting will be based on observation periods defined in [Section 2.1.1.5](#).

Safety summaries (tables, figures) will primarily be based on all data from the on-treatment period with the exception of baseline data which will also be summarized where appropriate (e.g. change from baseline summaries). In addition, a separate summary for death including on treatment and post treatment deaths will be provided. Following the last administration of study treatment, adverse events (including serious adverse events), and new antineoplastic therapies will be collected for a period of 150 days. Following start of new antineoplastic therapy only treatment related adverse events will be collected. Select summaries of related adverse events will be produced for the combined on-treatment and post-treatment periods (see Protocol Section 10.5.2.2).

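### SAP safety summaries for the six Japanese patients who started on NIR178 alone are not split at the first PDR001 dose, so two regimens share one column

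*SAP*

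**What the plan says.** The run-in objective (SAP 1.2, Table 1-1) has two targets: "To assess the preliminary safety, and PK of single agent NIR178 and in combination with PDR001 in Japanese patients". SAP 1.1 describes the patients treated before Protocol Amendment 6 as "3 with SA NIR178 80mg and 3 with SA NIR178 160mg, during Cycle 1 and with PDR001 initiated at the beginning of Cycle 2". Patients in the later 240 mg cohort receive both drugs from Cycle 1 Day 1.

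SAP 2.6.2 states: "Safety summaries (tables, figures) will primarily be based on all data from the on-treatment period". SAP 2.1.1.5 defines that period as running "from date of first administration of study treatment to 30 days after date of last actual administration of study treatment". Under SAP 2.1.1.2, first and last administration of study treatment are the dates on which a "non-zero dose of either component of the treatment (NIR178 or PDR001) was administered". The period therefore opens with NIR178 alone and closes 30 days after the last dose of either drug.

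The safety set (SAP 2.2.2) classifies each patient once, and SAP 2.1 defines a treatment group as a set of patients, not as a phase within a patient. SAP 2.6.2.6.3 applies the safety set to the run-in, with the wording "For Japanese safety run-in study, frequency, severity and seriousness of dose limiting toxicities, AEs, laboratory abnormalities and other safety parameters", and adds no rule for separating the phases.

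**The concern.** Followed as written, a run-in patient's Cycle 1 events on NIR178 alone and any later events on NIR178 plus PDR001 are counted in one 80 mg or 160 mg column. The same applies to worst post-baseline laboratory grades and shifts (SAP 2.6.2.5) and to notable ECG and vital-sign counts (SAP 2.6.2.6.1 and 2.6.2.6.2). The AE listing separates pre- and post-treatment onsets (SAP 2.6.2.1) but does not mark the start of PDR001.

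Protocol 2.2 makes "the safety of single agent NIR178 in Japanese patients in relation to that of non-Japanese patients treated at the same dose levels" the primary determinant of Japanese entry to the phase II study. The phase I study had its own single-agent groups at 80 mg and 160 mg, with three patients each (Protocol 1.2.1.4). A mixed column does not describe the single-agent regimen and does not isolate the combination, so neither half of the objective has its own AE or laboratory summary from these cohorts. Each cohort has three patients, so one patient with an event moves an incidence by 1/3, or 33 percentage points. The phase in which that event began therefore matters to the reader.

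**Working it through.** The plan states no figure on this point, so there is none to reproduce. The check has two parts.

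**1. Which summaries mix the regimens**

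- AEs by class, term and grade: whole on-treatment period, so mixed.
- Worst laboratory grade and shift: whole on-treatment period, so mixed.
- Notable ECG and vital-sign values: not split by phase, so mixed.
- DLTs: evaluated in Cycle 1 only (SAP 1.1.4; SAP section 3), so single-agent data in these two cohorts.
- ECG change from baseline: given by timepoint (SAP 2.6.2.6.1), so Cycle 1 timepoints can be read separately.
- 240 mg cohort: combination from the first dose, so there is nothing to split.

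**2. How much of the period follows the start of PDR001**

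Inputs: a cycle is 28 days (Protocol 6.1.1); PDR001 starts on Cycle 2 Day 1, which is study day 29; the on-treatment tail is 30 days (SAP 2.1.1.5). The number of cycles per patient is not given, so the day of last dose, L, is an assumption shown as a range.

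For a patient who enters Cycle 2:
- length of the on-treatment period = L + 30 days
- single-agent time = 28 days
- share after PDR001 starts = (L + 30 − 28)/(L + 30)
- the same without the tail = (L − 28)/L

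| Last dose | L | With tail | Without tail |
|---|---|---|---|
| Cycle 2 Day 1 | 29 | 31/59 = 53% | 1/29 = 3% |
| End of 2 cycles | 56 | 58/86 = 67% | 28/56 = 50% |
| End of 3 cycles | 84 | 86/114 = 75% | 56/84 = 67% |
| End of 4 cycles | 112 | 114/142 = 80% | 84/112 = 75% |
| End of 6 cycles | 168 | 170/198 = 86% | 140/168 = 83% |

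For a patient who stops in Cycle 1 without PDR001 the share is 0%. These are shares of time; the documents give nothing from which to derive a share of events.

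**The case against.** The strongest reply has four parts.

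*Combination data are included on purpose.* Protocol 2.2 says that the final safety analysis will use all available data, including the combination phase, and the objective covers both regimens. This stands: the fault is the missing split, not the inclusion.

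*The entry decision does not depend on these tables.* The rules in Protocol 4.1.4 turn on Cycle 1 DLTs and a review of all available data. Protocol 4.1.4 and SAP 1.1.4 both record that Japanese patients can join the other parts, and SAP section 4 says that the study is closed out. This also stands: a split cannot change that decision.

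*A reader can separate the phases by hand.* There are six patients, and both AEs and administered doses are listed. That is so, and it shows that the fix is cheap. It does not replace a prespecified summary with a denominator and exposure time.

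*The output shells are a separate document.* A split there cannot be excluded, but the SAP text defines no rule for one.

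A reader might also infer that rates in these columns are biased upward against the phase I single-agent patients. The documents do not support that. The SAP plans no formal comparison, and the phase I single-agent patients were dosed in 28-day cycles with no stated limit to one cycle. Restricting the Japanese patients to 28 days could bias incidence the other way.

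**Conclusion.** The point holds as a reporting gap. For the six patients who started on NIR178 alone, the planned AE, worst-grade laboratory and notable ECG or vital-sign summaries mix two regimens that the objective names separately. For a patient who enters Cycle 2, 53% to 86% of the on-treatment period follows the start of PDR001. That range assumes a last dose between Cycle 2 Day 1 and the end of Cycle 6 and counts the 30-day tail as time after PDR001 started.

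Three stronger readings go too far:
- That the single-agent objective is answered mostly with combination data. By time this depends on the assumed cycles and the tail (50% at two cycles without it), and by events it is unknown.
- That no output shows single-agent safety. The DLT summary does so for these cohorts, and ECG change by timepoint does so for Cycle 1.
- That the combination data are lost. They remain in the run-in summaries and listings, but not separately.

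**What to change.** Add a rule to SAP 2.6.2.6.3 for the 80 mg and 160 mg run-in cohorts. Report AEs by onset, and worst laboratory, ECG and vital-sign values by date, in two windows:

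- (a) from the first NIR178 dose to before the first PDR001 dose, or to the end of the on-treatment period for a patient who never receives PDR001;
- (b) from the first PDR001 dose onward.

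Give each window its own denominator and exposure time. Keep the overall column and the original study baseline. State how Cycle 2 Day 1 values taken before the infusion are assigned.

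Clarify one related wording at the same time. The run-in full analysis set requires a dose of the assigned combination (SAP 2.2.1), and the safety set is drawn from it (SAP 2.2.2), whereas SAP Table 2-2 refers to a dose of either drug. Read literally, SAP 2.2.1 could remove from window (a) a patient who stopped before PDR001.

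The cost is SAP text and a few extra columns for six patients, from dates already collected. The cells will be very small. A footnote should say that onset after PDR001 starts does not by itself attribute an event to PDR001, because NIR178 continues and Cycle 1 exposure may contribute.
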